**Table 6 Event and Censoring Rules for IMV/ECMO**

	Situation	Date of Event or Censoring
IMV/ECMO or Death Event	IMV/ECMO documented in the clinical status form (6)	Earliest date when IMV/ECMO is observed
	Death	Date of death if no IMV/ECMO was observed
Censor	No post-baseline clinical status assessments	Randomization date
	No IMV/ECMO or death by Day 28	Date of last clinical status assessment
	Lost to follow-up	Date of last clinical status assessment
The rules apply to dates up to study Day 28 +2 day window (Day 30).		

Kaplan-Meier methods will be used to estimate the time to IMV/ECMO or death by treatment arm. Summary statistics, including median time to IMV/ECMO or death and corresponding

95% confidence intervals, will be presented by treatment arm. The time to IMV/ECMO or death will be analyzed using the log-rank test stratified by age (< 60 years versus  $\geq$  60 years) and baseline 7-point clinical status scale (baseline 3 or 4 versus 5).

The hazard ratio (HR) of the time to IMV/ECMO or death by treatment arm will be estimated using a stratified Cox proportional hazards model stratified by age (< 60 years versus  $\geq$  60 years) and baseline 7-point clinical status scale (baseline 3 or 4 versus 5).

Kaplan-Meier plots of the time to improvement in clinical status will be generated by treatment arm.

The clinical status assessments will be listed.

#### **7.4.2 Secondary Efficacy Analysis**

##### **7.4.2.1 Number of Ventilator-Free Days**

The number of ventilator-free days will be presented by treatment arm using descriptive statistics. The 95% confidence intervals will be provided. The treatment arm comparison will be performed using the Wilcoxon rank sum test.

In addition, the number of patients that remain ventilator-free for certain clinically significant thresholds (e.g. 21 days) may be summarized.

##### **7.4.2.2 Mortality Rate at Day 15 and 28**

The Day 15 and Day 28 mortality rates and associated 95% confidence interval will be summarized by treatment arm.

The mortality rate at Day 15 and Day 28 will be compared between treatment arms using the CMH test stratified by age (< 60 years versus  $\geq$  60 years) and baseline 7-point clinical status scale (baseline 3 or 4 versus 5). The point estimates and 95% confidence intervals of the mortality rates at Day 15 and Day 28 will be presented by treatment arm. The CMH odds ratio, difference in mortality rates at Day 15 and Day 28, and associated 95% confidence intervals will be presented.

##### **7.4.2.3 Clinical Status**

The clinical status at Day 8 (+/- 1 day), Day 15 (+/- 1 day), Day 22 (+/- 1 day), and Day 28 (+/- 2 day) will be summarized by treatment arm using counts and percentages.

Clinical status assessments will be listed by patient.

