### **2.3.2 *Secondary Objectives***

1. To compare the number of ventilator-free days, defined as the number of days that patients are alive and not intubated, from randomization to Day 28 between pacritinib + SOC versus placebo + SOC
2. To compare the mortality rate between pacritinib + SOC versus placebo + SOC at Day 28
3. To compare the mortality rate between pacritinib + SOC versus placebo + SOC at Day 15
4. To compare the time to improvement by at least 2 points relative to Baseline on the 7-point ordinal scale of clinical status between pacritinib + SOC versus placebo + SOC
5. To compare the clinical status assessed by the 7-point ordinal scale of clinical status at Days 8, 15, 22, and 28 between pacritinib + SOC versus placebo + SOC
6. To compare the rate of use of immunomodulatory agents as treatment for COVID-19 during the 28 days following randomization between pacritinib + SOC versus placebo + SOC
7. To evaluate the toxicity profile of pacritinib therapy in hospitalized patients with severe COVID-19 with or without cancer

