## **7 STUDY ASSESSMENTS**

### **7.1 Criteria for Evaluation**

#### **7.1.1     *Efficacy***

##### **7.1.1.1     *7-Point Ordinal Scale of Clinical Status***

The following 7-point ordinal scale of clinical status ([Cao et al 2020](#)) will be used to assess the ordinal scale secondary endpoints. The ordinal scale score is to be documented daily on study through Day 28 for all patients, including those who have been discharged from the hospital.

1. Not hospitalized with resumption of normal activities
2. Not hospitalized but unable to resume normal activities
3. Hospitalization, not requiring supplemental oxygen
4. Hospitalization, requiring supplemental oxygen not meeting criteria for categories 5 or 6
5. Hospitalization, on non-invasive positive pressure ventilation or high-flow nasal cannula

6. Hospitalization, requiring IMV and/or ECMO
7. Death

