#### 7.1.4.8 *Outpatient Assessments*

- 7-point ordinal scale of clinical status (Daily scores through Day 28 will be evaluated and will be based on weekly assessments performed on Day 8, Day 15, Day 22, and Day 28 [ $\pm 2$  days].)
- Documentation of pacritinib/placebo dosing for patients who continue treatment after discharge from the hospital
- AEs (will be documented through 30 days after the last dose of pacritinib/placebo and will be based on weekly assessments [ $\pm 2$  days] through 30 days after last dose)

- Concomitant medications (will be documented through 30 days after the last dose of pacritinib/placebo and will be based on weekly assessments [ $\pm 2$  days] through 30 days after last dose)

Note: Outpatient assessments should be based on weekly telephone/videoconference communication with the patient and include an evaluation of the **daily** 7-point ordinal scale score for the days between contacts and daily pacritinib/placebo dosing as outlined in [Table 1](#). More frequent telephone/videoconference contact may occur as needed to supplement the above assessments. Review of medical records may also be performed as needed to supplement these assessments; medical records should be reviewed for patients who cannot be reached by telephone/videoconference.

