### **Secondary Endpoints**

The number of ventilator-free days will be presented by treatment arm using descriptive statistics including mean, median, standard deviation, interquartile range, and may include frequency distributions.

The mortality rate at Day 28 will be compared between treatment arms using the CMH test stratified by age (< 60 years versus  $\geq$  60 years) and baseline 7-point clinical status scale (baseline 3 or 4 versus 5). The point estimates and 95% confidence intervals of the mortality rates at

Day 28 will be presented by treatment arm. The CMH odds ratio, difference in mortality rates at Day 28, and associated 95% confidence intervals will be presented.

The mortality rate at Day 15 will be compared between treatment arms using the CMH test stratified by age (< 60 years versus  $\geq$  60 years) and baseline 7-point clinical status scale (baseline 3 or 4 versus 5). The point estimates and 95% confidence intervals of the mortality rates at Day 15 will be presented by treatment arm. The CMH odds ratio, difference in mortality rates at Day 15, and associated 95% confidence intervals will be presented.

The time from randomization to improvement by at least 2 points relative to Baseline on the 7-point clinical status will be compared between treatment arms using a stratified log-rank test stratified by age (< 60 years versus  $\geq$  60 years) and baseline 7-point clinical status scale (baseline 3 or 4 versus 5). All enrolled patients will have a score between 3 and 5 by virtue of being hospitalized and non-intubated; therefore, patients who progress from 3 to 1, from 4 to 2, or from 5 to 3 will have met the definition of improvement. Kaplan-Meier methods will be used to estimate time to improvement by treatment arm. Summary statistics, including median time to improvement and corresponding 95% confidence intervals, will be presented by treatment arm. The hazard ratio (HR) for time to improvement by treatment arm will be estimated using a stratified Cox proportional hazards model stratified by age (< 60 years versus  $\geq$  60 years) and baseline 7-point clinical status scale (baseline 3 or 4 versus 5).

The clinical status assessed by the 7-point ordinal scale of clinical status at Days 8, 15, 22, and 28 will be presented by treatment arm using counts and percent of patients at each level of the 7-point scale score.

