### 2.2 Secondary Objectives

1. To compare the number of ventilator-free days, defined as the number of days that patients are alive and not intubated, from randomization to Day 28 between pacritinib + SOC versus placebo + SOC
2. To compare the mortality rate between pacritinib + SOC versus placebo + SOC at Day 28
3. To compare the mortality rate between pacritinib + SOC versus placebo + SOC at Day 15
4. To compare the time to improvement by at least 2 points relative to Baseline on the 7-point ordinal scale of clinical status between pacritinib + SOC versus placebo + SOC
5. To compare the clinical status assessed by the 7-point ordinal scale of clinical status at Days 8, 15, 22, and 28 between pacritinib + SOC versus placebo + SOC
6. To compare the rate of use of immunomodulatory agents as treatment for COVID-19 during the 28 days following randomization between pacritinib + SOC versus placebo + SOC
7. To evaluate the toxicity profile of pacritinib therapy in hospitalized patients with severe COVID-19 with or without cancer

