#### **6.2.4    Ordinal Scale of Clinical Status**

The clinical status adapted from [Cao et al.](#) (as described in [Table 3](#)), will be a secondary efficacy outcome variable. The 7-point clinical status score at Day 8, 15, 22 and 28 will be presented by treatment arm using the ITT population.

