### 7.1 General Statistical Considerations

Unless specified otherwise, the analyses of data collected will be descriptive and summaries will be presented separately for each treatment arm and in total for the specified analysis population. Statistical analyses will be descriptive and no formal hypothesis testing or comparative analyses between treatment arms will be performed unless stated. Confidence intervals (CIs) will be constructed at the 95% confidence level where appropriate. For categorical variables, confidence intervals will be calculated using the Clopper-Pearson method where appropriate.

For continuous variables, the number of observations (n), mean, standard deviation, median, q1, q3, minimum, and maximum will be provided as summary statistics. For categorical variables, the frequency and percentage in each category will be displayed.

Summary tables will in general display 2 treatment arms:

- Pacritinib 400 mg
- Placebo

A total column will be added for table summaries if appropriate.

Efficacy analyses will in general be based on the ITT Population according to the randomized (planned) treatment arm.

Safety analyses will in general be performed using the Safety Population according to the treatment actually received.

Subject disposition, demographics, and clinical baseline characteristics data will be summarized for the ITT Population. If the ITT Population differs from other defined analysis populations, additional patient characteristic summaries may be generated using other analysis populations.

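### Secondary objective 5 is to compare 7-point clinical status between arms at four days, but neither document plans a between-arm analysis of it (minor)

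*SAP*

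**What the plan says.** **Objective.** SAP 2.2, item 5, reads "To compare the clinical status assessed by the 7-point ordinal scale of clinical status at Days 8, 15, 22, and 28". Protocol 2.3.2 has the same item, ending "clinical status at Days 8, 15, 22, and 28 between pacritinib + SOC versus placebo + SOC", and the protocol synopsis repeats it.

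**Analysis.** Protocol 11.3 says that clinical status "will be presented by treatment arm using counts and percent of patients at each level of the 7-point scale score". SAP 6.2.4 says that the score "will be presented by treatment arm using the ITT population". SAP 7.4.2.3 sets windows around the four days and says that status "will be summarized by treatment arm using counts and percentages". SAP 7.1 adds the default that "no formal hypothesis testing or comparative analyses between treatment arms will be performed unless stated".

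**Data.** Protocol 7.1.1.1 states: "The ordinal scale score is to be documented daily on study through Day 28 for all patients". This includes discharged patients, for whom protocol 7.1.4.8 says: "Daily scores through Day 28 will be evaluated and will be based on weekly assessments performed on Day 8" and the later weekly contacts.

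**Related test.** SAP 7.4.2.1 compares ventilator-free days by a Wilcoxon rank sum test and names no strata. Protocol 11.3 plans descriptive statistics only for that endpoint. SAP section 9 declares no change from the protocol analysis.

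**The concern.** The objective asks for a contrast between arms, and the analysis gives two columns of percentages. There are seven levels, two arms and four days, so the reader receives 7 × 2 × 4 = 56 percentages. No effect measure or interval summarizes them. Under SAP section 1, any comparison added later must be labelled post hoc, so the objective as worded would have no prespecified answer.

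What is at stake is one Phase 2 secondary objective. The primary endpoint and its analysis do not depend on it.

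**Working it through.** **1. Objectives against SAP analyses.** SAP 2.2 lists seven secondary objectives. The first six use the verb compare; the seventh, on toxicity, uses evaluate.

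| Objective | SAP section | Between-arm analysis |
|---|---|---|
| 1 Ventilator-free days | 7.4.2.1 | Wilcoxon rank sum test |
| 2, 3 Mortality at Days 28 and 15 | 7.4.2.2 | Stratified CMH test, odds ratio, difference, CI |
| 4 Time to 2-point improvement | 7.4.2.4 | Stratified log-rank test, Cox hazard ratio |
| 5 Status at Days 8, 15, 22, 28 | 7.4.2.3 | None |
| 6 Immunomodulatory agents | 7.4.2.5 | Stratified CMH test, odds ratio, difference, CI |

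Objective 5 is the exception. The verb is not used loosely: the tertiary markers and the toxicity objective use evaluate, and their analyses are descriptive.

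**2. Is the full scale compared elsewhere?** Only in parts. The primary analysis uses level 6 or 7 at any time up to Day 28. Mortality uses level 7 at Days 15 and 28. Ventilator-free days count days at level 5 or less. Time to improvement uses the first 2-point drop. None compares all seven levels on a named day.

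**3. What a comparison would deliver.** Neither document gives power for this endpoint, so the only figure to reproduce is the sample size. With 13.5% versus 26.5%, one-sided 0.10 and 80% power:

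n = [1.2816·√(2·0.20·0.80) + 0.8416·√(0.135·0.865 + 0.265·0.735)]² / 0.13² = 84.5, so 85 per arm.

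The continuity correction raises this to 100 per arm, which matches the stated 200.

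The rest is illustrative. Five placebo distributions are assumed (levels 1 to 7, in %). The pacritinib distribution follows from multiplying the odds of a worse status by 0.6. With p̄ the mean of the two arms at each level and N = 200:

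- V = N(1 − Σp̄³)/12, and SE = 1/√V
- 95% CI = exp(ln 0.6 ± 1.96·SE)
- power = Φ(0.511/SE − z), with z = 1.96 (two-sided 0.05) or 1.2816 (one-sided 0.10)

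For the first row the pacritinib arm is 47.3/21.5/4.3/6.4/3.0/8.5/8.9. Then Σp̄³ = 0.083, V = 200·0.917/12 = 15.28 and SE = 0.256.

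| Assumed placebo distribution | SE | 95% CI | Power, two-sided 0.05 | Power, one-sided 0.10 |
|---|---|---|---|---|
| 35/22/5/8/4/12/14 | 0.256 | 0.36–0.99 | 52% | 76% |
| 60/15/3/4/2/6/10 | 0.290 | 0.34–1.06 | 42% | 68% |
| 20/30/8/12/6/12/12 | 0.251 | 0.37–0.98 | 53% | 77% |
| 15/30/8/15/7/15/10 | 0.251 | 0.37–0.98 | 53% | 78% |
| 3/15/15/32/15/15/5 | 0.251 | 0.37–0.98 | 53% | 78% |

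As a check on the first row, 300 fitted models with two binary strata gave a mean SE of 0.264 and 95% coverage. The upper limit is then 0.6·exp(1.96·0.264) = 1.01, so it sits at about 1.

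**4. Ventilator-free days.** Simulated trials (6,000 per scenario, N = 200, assumed stratum progression rates, progression odds ratio 0.43, one-sided 0.10) gave:

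| Stratum rates | Power, Wilcoxon | Power, van Elteren | Null rejection, Wilcoxon | Null rejection, van Elteren |
|---|---|---|---|---|
| 10/22/33/55% | 82.0% | 82.9% | 8.9% | 10.3% |
| 14/23/30/45% | 83.3% | 83.8% | 9.7% | 10.3% |
| 18/24/28/36% | 83.7% | 83.9% | 10.6% | 10.8% |

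The gains are 0.9, 0.5 and 0.2 points. Part of the largest gain reflects the unstratified test being slightly conservative when the strata are strongly prognostic. Allowing for other inputs, about 0 to 1.5 points is a fair range.

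**The case against.** The strongest defence is that the plan is deliberate. Protocol section 11 says that ordinal variables are summarized by frequency distributions, summary statistics or shift tables, and protocol 11.3 and the SAP follow that rule. On this view the only slip is one verb in a Phase 2 secondary objective, and the post hoc label in SAP section 1 is itself a safeguard. It stands that the two documents agree on the analysis. It does not remove the conflict with their shared objective, but it does limit the weight.

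Several stronger readings are tempting, and the documents do not support them.

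- **The scale is never compared.** It is, in parts. Mortality at Days 15 and 28 is a stratified comparison of level 7 on two of the four named days.
- **The tables will produce false positives.** If a 95% interval were put on each of the seven level differences, at least one would exclude zero in 28 to 30% of trials with no effect on a single day. No such intervals are planned, and SAP 7.1 excludes them.
- **The tables are defective in denominator, score selection or deaths.** Each window holds at least three daily scores and no selection rule is given, but SAP 8.2 leaves table format to a programming specification that is not available here. Death is level 7 of a scale recorded for all patients, so leaving deaths out would be a strained reading. These are details to state, not errors.
- **The Wilcoxon test is wrong.** It is valid without strata.

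**Conclusion.** The point holds and is minor. Objective 5 asks for a comparison of the full scale on four days. The plan contains none, and its default rule prevents one from being assumed. This follows from the text and needs no numerical assumption. The primary conclusion is unaffected.

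The figures for the missing analysis rest on assumed distributions, 100 scored patients per arm, proportional odds and a true odds ratio of 0.6. They show a usable but imprecise estimate, with an upper confidence limit close to 1, so it should not be presented as confirmatory. The stratified test of ventilator-free days is a consistency improvement with little effect on power.

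**What to change.** **SAP 7.4.2.3.** Add, at each of Days 8, 15, 22 and 28, a proportional-odds model with treatment and the two randomization factors as entered in the IXRS. Report the common odds ratio and 95% CI. Name one day in advance as the key day, for example Day 28, because four odds ratios without a key day would again leave the choice open. Label all results non-confirmatory. State that:

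- patients who died on or before the nominal day are scored 7;
- the score closest to the nominal day is used;
- missing scores are reported by arm.

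**SAP 7.4.2.1.** Replace the Wilcoxon test with the van Elteren test stratified by age and baseline status. This matches the randomization and the other SAP efficacy tests.

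**SAP section 9.** Record both changes, and also the ventilator-free-days test itself, which protocol 11.3 does not contain.

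**Cost.** SAP text and a few lines of code; the scores and strata are already collected. The downside is one extra non-confirmatory analysis that relies on proportional odds. If only description is wanted, objective 5 could be reworded in both documents. That costs more, because protocol section 16 requires an amendment with ethics approval.

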#### 7.4.2.4 Time to Improvement in Clinical Status

Time to improvement in clinical status is defined as the first ordinal scale assessment with 2 points reduction from the baseline clinical status assessment. Patients not known to have improved by Day 28 will be censored at the date of their last clinical status assessment. Patients who have died will be censored at Day 28. Table 7 provides the rules for improvement in clinical status and censoring for the time to event analysis

**Table 7 Event and Censoring Rules for Improvement in Clinical Status**

	Situation	Date of Event or Censoring
2-point reduction from baseline in the clinical status form (event)	2-point reduction from baseline documented in the clinical status form	Earliest date when a 2-point reduction from baseline in the clinical status form is observed
Censor	Death	Day 28
	No post-baseline clinical status assessments	Randomization Date
	No 2-point reduction from baseline	Date of last clinical status assessment
	Lost to follow-up	Date of last clinical status assessment

The rules apply to dates up to study Day 28 +2 day window (Day 30).

Kaplan-Meier methods will be used to estimate time to improvement by treatment arm. Summary statistics, including median time to improvement and corresponding 95% confidence intervals, will be presented by treatment arm. The time to improvement will be analyzed using the log-rank test stratified by age (< 60 years versus  $\geq 60$  years) and baseline 7-point clinical status scale (baseline 3 or 4 versus 5).

The hazard ratio (HR) for time to improvement by treatment arm will be estimated using a stratified Cox proportional hazards model stratified by age (< 60 years versus  $\geq 60$  years) and baseline 7-point clinical status scale (baseline 3 or 4 versus 5).

Kaplan-Meier plots of the time to improvement in clinical status will be generated by treatment arm.

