## **Secondary Endpoints**

1. The number of ventilator-free days, defined as the number of days that patients are alive and not intubated, from randomization to Day 28
2. The mortality rate at Day 28 is defined as the number of patients with outcome of death during the 28 days following randomization divided by the total number of patients in the ITT population
3. The mortality rate at Day 15 is defined as the number of patients with outcome of death in the 15 days following randomization divided by the total number of patients in the ITT population.
4. The time to improvement by at least 2 points relative to Baseline on the 7-point ordinal scale of clinical status. All enrolled patients will have a score between 3 and 5 by virtue of being hospitalized and non-intubated; therefore, patients who progress from 3 to 1, from 4 to 2, or from 5 to 3 will have met the definition of improvement.
5. The clinical status as assessed by the 7-point ordinal scale of clinical status at Days 8, 15, 22, and 28.
6. The rate of use of immunomodulatory agents as treatment for COVID-19 is defined as the proportion of patients reporting use of medications such as corticosteroids, tocilizumab, anakinra, or eculizumab as treatment for COVID-19, during 28 days following randomization divided by the patients in the ITT population.

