**Table 3 Ordinal Scale of Clinical Status (adapted from Cao et al.)**

Ordinal Value and Description
1. Not hospitalized with resumption of normal activities
2. Not hospitalized but unable to resume normal activities
3. Hospitalization, not requiring supplemental oxygen
4. Hospitalization, requiring supplemental oxygen not meeting criteria for categories 5 or 6
5. Hospitalization, on non-invasive positive pressure ventilation or high-flow nasal cannula
6. Hospitalization, requiring IMV and/or ECMO
7. Death

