### **6.1 Primary Efficacy Endpoint**

The primary endpoint is the proportion of patients with progression to IMV and/or ECMO or death by Day 28 (+/- 2 days) for the Intent-to-Treat (ITT) Population. Patients will be considered to have progression to IMV and/or ECMO or death based on the [Cao et al. \(Table 3\)](#) clinical status assessment of 6 or 7. Specifically, the proportion of patients with progression to IMV and/or ECMO or death by Day 28 (+/- 2 days) will be calculated in each treatment arm as:

- (Number of patients with clinical status of 6 or 7 at any time on or before Day 28 (+/- 2 days)) / (Number of patients in the ITT population)

Patients who discontinued early and did not progress to IMV and/or ECMO or death (a clinical status of 6 or 7) will be considered as having progression unless they were discharged from the clinical facility (discharge date is not missing), in which case they will be considered non-progression.

Patients will be summarized based on the randomized (planned) treatment arm. Patients can meet this endpoint in two ways by progressing to IMV and/or ECMO or dying.

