## 6.2 Secondary Efficacy Endpoints

### 6.2.1 Number of Ventilator-Free Days

The number of total ventilator-free days is defined as the number of total days that patients are alive and not intubated, from Day 1 to Day 28. The number of total ventilator-free days will be calculated as:

- Number of ventilator free days = Number of total days with clinical status assessment of 5 or less from Day 1 until Day 28

Ventilator-free days includes all episodes a patient is not on IMV and/or ECMO and report a clinical status form of 5 or less from Day 1 to Day 28.

Patients who discontinued early will be considered as being ventilator-free up to Day 28 if they were discharged from the clinical facility (discharge date is not missing), in which case they will be considered as not having an event of IMV and/or ECMO up to Day 28. Patients who discontinued early and were not discharged from the clinical facility will be considered as being ventilator-free up to the time of study discontinuation.

### 6.2.2 Mortality Rate at Days 15 and 28

The 15-day mortality rate is defined as the proportion of patients with outcome of death during the 15 days following randomization. The Day 15 mortality rate is calculated as:

- $(\text{Number of patients that die by Day 15}) / (\text{Number of patients in the ITT population})$

The 28-day mortality rate is defined as the proportion of patients with outcome of death during the 28 days following randomization. The Day 28 mortality rate is calculated as:

- $(\text{Number of patients that die by Day 28}) / (\text{Number of patients in the ITT population})$

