### **7.1.4 Handling of Dropouts or Missing Data**

Unrecorded data values will be recorded as missing. Only recorded (i.e. complete) data values will be used for statistical analyses. In general, invalid or missing values will not be imputed in the data unless stated otherwise.

In addition, analysis methods for handling dropouts are specified under the endpoint definition.

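### Time to improvement has no discharge-date rule, so some baseline-4 or baseline-5 patients discharged alive can be censored as unimproved on the day they meet the endpoint

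*SAP*

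**What the plan says.** **Endpoints that use the discharge date.** For the primary endpoint (SAP 6.1, repeated in 7.4.1), an early leaver without a score of 6 or 7 counts as progressed "unless they were discharged from the clinical facility (discharge date is not missing), in which case they will be considered non-progression". For ventilator-free days (SAP 6.2.1): "Patients who discontinued early will be considered as being ventilator-free up to Day 28 if they were discharged from the clinical facility".

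**Time to improvement.** SAP 6.2.3 takes the first assessment with a drop of 2 or more points. SAP Table 7 defines the event as "2-point reduction from baseline documented in the clinical status form". SAP 7.4.2.4 adds: "Patients not known to have improved by Day 28 will be censored at the date of their last clinical status assessment". Death has its own rule: "Patients who have died will be censored at Day 28". Discharge has none. SAP 7.1.4 leaves a programmer no room to supply one: "In general, invalid or missing values will not be imputed in the data unless stated otherwise".

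**The scale.** In SAP Table 3 the only scores for a living patient outside hospital are 1 and 2, the latter being "Not hospitalized but unable to resume normal activities". Protocol 11.1.1 fixes the thresholds: "patients who progress from 3 to 1, from 4 to 2, or from 5 to 3 will have met the definition of improvement".

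**Collection of scores.** Protocol 7.1.4.7 requires a score on the day of discharge. After that, daily scores through Day 28 come from weekly contacts (Protocol 7.1.4.8 and Table 1 note 3), with medical records to be reviewed when a patient cannot be reached. Neither document says whether the discharge-day score describes the patient before or after leaving.

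**The concern.** One discharge date can make a patient a non-progressor in the primary analysis and ventilator-free to Day 28, while the same patient is unimproved in time to improvement. For baseline 4, and for baseline 5 not yet at 3, the fact that ends observation (leaving hospital alive) is also the fact that meets the endpoint. Censoring there is informative, because Kaplan-Meier and Cox methods assume that a censored patient has the same future chance of improving as those still at risk, whereas this patient has already improved.

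At stake are the planned Kaplan-Meier curve and median, the stratified log-rank test and the stratified Cox hazard ratio for one of six secondary efficacy endpoints. The primary test and the sample size are not affected.

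**Working it through.** **1. The plan's own figure.** No event rate, power or size is stated for time to improvement. The only design figure is about 200 patients for the primary endpoint. With 26.5% versus 13.5% and one-sided alpha 0.10, the pooled formula gives n = [1.2816·√(2·0.20·0.80) + 0.8416·√(0.265·0.735 + 0.135·0.865)]² / 0.13² = 84.5 per arm. With continuity correction, (84.5/4)·[1 + √(1 + 4/(84.5·0.13))]² ≈ 99.3, so 100 per arm and 200 in total. This reproduces the plan and is used below only as the trial size.

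**2. Table 7 applied to each case.** The patient is discharged alive and has no later score.

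| Baseline | Forms on file | What discharge implies | Table 7 result |
|---|---|---|---|
| 4 | discharge-day form reads 1 or 2 | improved | event, correct |
| 4 | last form reads 3 or 4 | score ≤ 2, drop ≥ 2, improved | censored at last form, wrong |
| 5 | a 3 was already recorded in hospital | improved earlier | event, correct |
| 5 | last form reads 4 or 5, no earlier 3 | score ≤ 2, drop ≥ 3, improved | censored at last form, wrong |
| 3 | last form reads 3 | score 1 or 2; only 1 is improvement | censored, correct unless a 1 is known |

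The fault lies in the second and fourth rows. It needs a discharge-day form that still shows inpatient status and no later score, for example after consent is withdrawn for all procedures (Protocol 4.2).

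**3. Size under equal loss.** Let q be the share of improvements that occur at discharge and m the share of those with no form showing them. The lost share of events is L = q·m. If patients who have not improved stay at risk to Day 28, the observed hazard is multiplied by (1 − L), so the observed curve is about S(t)^(1 − L). Neither q nor m is in the documents.

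*Model A (assumed: 78% improved by Day 28, q = 0.85).* The true Day 28 value of S is 0.22. The standard error at 100 per arm is √(0.78·0.22/100) = 4.1 points.

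| m | L | 1 − 0.22^(1−L) | Fall |
|---|---|---|---|
| 2% | 0.017 | 77.4% | 0.6 points |
| 10% | 0.085 | 75.0% | 3.0 points |
| 20% | 0.170 | 71.5% | 6.5 points |

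Simulated trials of 100 per arm gave falls of about 0.4, 3.1 and 6.6 points. At 10% the simulated median moved from 11 to 12 days.

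*Model B (assumed: exponential improvement with a 10-day median before deaths, 10% deaths held at risk to Day 28, q = 0.80).* Events without loss: 200·0.9·(1 − 2^−2.8) = 154. Multiplying by (1 − 0.8m) gives 148, 142 and 129 at m = 5%, 10% and 20%. The median solves 0.1 + 0.9·2^(−t/10) = 0.5, so t = 11.7 days. At m = 10% the true curve must fall to 0.5^(1/0.92) = 0.471, so t = 12.8 days. In whole-day simulation the move was from 12 to 14.

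**4. Hazard ratio (pacritinib to placebo, no true effect).** The observed ratio is about (1 − L for pacritinib)/(1 − L for placebo), which is 1 whenever loss is equal.

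| m, pacritinib vs placebo | q | Formula | Simulated |
|---|---|---|---|
| 10% vs 10% | 0.80 | 1.00 | 0.99 |
| 10% vs 5% | 0.80 | 0.92/0.96 = 0.96 | 0.95 |
| 20% vs 10% | 0.80 | 0.84/0.92 = 0.91 | 0.90 |
| 10% vs 20% | 0.80 | 0.92/0.84 = 1.10 | 1.09 |
| 2% vs 5% | 0.85 | 0.983/0.9575 = 1.03 | 1.04 (1.01 with no loss) |
| 5% vs 15% | 0.85 | 0.9575/0.8725 = 1.10 | 1.11 |

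The two-sided 5% log-rank test rejected in about 5% of trials at 2% versus 5%, and in about 9% at 5% versus 15%.

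**The case against.** The strongest reply is that the protocol already closes most of this path. A score is required on the discharge day; if it reads 1 or 2, the event is on file and no later form is needed. For patients who cannot be reached, the hospital record shows the discharge, and that is enough to support a score of 2 or less. This stands, and it limits the problem to patients with an inpatient discharge-day score for whom no later score is obtained, mainly those who withdraw consent or whose site skips the record review. It does not remove the problem, because the meaning of the discharge-day score is undefined. Several other items collected that day ask for the lowest saturation or the highest oxygen support, so a ward score is plausible.

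A second reply is that the primary and ventilator-free-day rules serve a binary and a count endpoint, which need a value for every patient, and that the SAP's other time-to-event analysis (Table 6) also has no discharge rule. That is true, but in Table 6 discharge is not the event being counted. Here it can be.

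A reader might infer that every discharged patient without a post-discharge form is wrongly censored. The documents do not support that: a discharge-day score of 1 or 2 captures the event, some baseline-5 patients already have it, and a baseline-3 patient discharged at score 2 has not improved. A reader might also infer that the treatment comparison is biased. That needs loss to differ between arms, and nothing in the documents of this double-blind trial indicates such a difference.

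**Conclusion.** The gap is real and narrow. A stated rule gives the wrong result for baseline 4, and for baseline 5 not yet at 3, when discharge is known but the last form still shows inpatient status. How many patients this affects cannot be found in the documents and may be small.

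On the assumed models, a 2% loss is negligible (about half a point at Day 28). An equal 10% loss costs about 3 points, roughly 0.7 of one standard error, and 1 to 2 days on the median, while the hazard ratio stays about 1. The larger hazard-ratio shifts and the 9% rejection rate rest on unequal losses that were chosen for illustration. They show which way the bias would go and are not forecasts. The change is worth making because it is cheap and removes a conflict between endpoints, but it concerns a secondary endpoint only.

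**What to change.** In SAP 6.2.3, 7.4.2.4 and Table 7:

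- For baseline 4 or 5, date improvement at the earlier of the first form with a drop of 2 or more points and the date of alive discharge. Exclude transfer to another hospital or to hospice where that is known.
- For baseline 3, keep requiring a recorded score of 1.
- State whether the discharge-day score describes status before or after leaving.
- Keep the form-only rule as a sensitivity analysis, and report by arm how many events rest on the discharge date alone. That count supplies the figure now missing.

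The cost is SAP wording and one derivation from a date that the SAP already uses elsewhere. The downside is that discharge destination must be checked for the few patients with no post-discharge score, and it is not among the listed assessments. The change should be made before unblinding.
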